## 8.2 Insurance Coverage

Channel Medsystems, Inc. maintains clinical trial insurance coverage for this study in accordance with the laws and regulations of the country in which the study it is being performed. Documentation will be provided upon request.

## 8.3 Potential Benefits to the Subject

It is possible that Subject will not receive any benefits from treatment with the Cerene Device. Potential benefits of treatment that may be realized by study participants include overall fewer symptoms related to heavy menstrual bleeding and improved quality of life. In addition, subjects participating in the study is the ability to learn more about their heavy menstrual bleeding, based on the assessments that will be performed throughout the course of the study. In addition, the subjects will receive education about the monitoring of their disease, as will be required for study participation.

## 9 Study Monitoring

In accordance with applicable regulations, GCP, and Sponsor procedures, when subject enrollment is initiated, study monitors will meet with clinical site staff to review the protocol, subject eligibility criteria, study requirements, data collection and reporting requirements, and the investigator's responsibilities to satisfy regulatory, ethical, and Sponsor's requirements. The study monitor will identify the types and location of source documentation in use at the site.

The study monitor will monitor study data to verify that the subject's rights and well-being are protected, the study investigator is conducting the study in compliance with the protocol and the investigator's agreement, and to ensure reported data are authentic, accurate and complete. Remote and on-site data monitoring will be utilized. It is the Investigator's responsibility to ensure the accuracy, completeness, and timeliness of the data reported in the subject's CRF.

The Investigator will allow direct access to subject files and source documents for the purpose of verifying CRF entries and assist with the study monitor's activities as required. Clinical site staff will provide adequate time, office accommodations, and resources (including copy machine, phone, and/or internet access) to the study monitor for monitoring visits. Source documentation supporting the CRF data should indicate the subject's participation in the study and should document the dates and details of study procedures, AEs, and subject status. Source documents must be signed and dated by the investigator or designee for each visit.

A third-party monitor has been appointed as the data management CRO for this study.

Study Monitor:

[REDACTED]

## 9.1 Responsibilities of the Sponsor

Sponsor responsibilities include but are not limited to:

- Conducting this clinical study in compliance with all applicable regulatory requirements and guidelines, specifically in accordance with FDA regulations as described in 21 CFR 50 and 56 and 812, ISO 14155:2011(E) Clinical investigation of medical devices for human subjects – Good clinical practice, IRB/EC requirements, and the Informed Consent provisions of the Declaration of Helsinki.
- Ensuring study oversight.
- Monitoring study data to verify that the subject's rights and well-being are protected.
- Informing the clinical investigator of any new information about the study that may affect the health, safety or welfare of the subjects, or which may influence her decision to continue participating in the study.
- Providing the clinical investigator with the study protocol and the CRFs on which to document the study evaluation variables for each subject.
- Selecting qualified investigators to conduct this clinical study. Each Investigator will sign an Investigator Agreement prior to the study start. Financial Disclosure Statements will be completed, as required.
- Maintaining copies of correspondence, records of shipment and disposition of devices, adverse device effects, records related to the signed investigator agreements, and other records related to the clinical study.

## 9.2 Responsibilities of the Investigator

Each clinical investigator that will perform treatments with the investigational device in this clinical study must be licensed a physician in his/her country of employment. The investigator will affirm by his/her signature on the Investigator's Agreement that he/she will fulfill his/her responsibilities to this clinical study.

Investigator responsibilities include but are not limited to:

- Protecting the rights, safety, and welfare of subjects under his/her care
- Ensuring that all subjects meet eligibility criteria prior to treatment
- Obtaining initial and ongoing IRB/EC Approval of the protocol
- Obtaining subject informed consent using an IRB/EC approved informed consent form
- Performing subject evaluations and reporting data as specified in the protocol
- Documenting and reporting protocol deviations
- Retaining original records for the timeframe required by local regulation or longer per Sponsor instruction
- Ensuring investigational devices are dispensed only to study subjects and under the direct supervision of the investigator or co-investigators
- Maintaining records of investigational device disposition

## 10 Record Keeping and Report Requirements

### 10.1 Subject Confidentiality

Subject confidentiality shall be maintained at all times throughout the conduct of the study, and all subject data shall be maintained secure against unauthorized access. Whenever possible, subject names will not be provided to the Sponsor. Only the study ID number will be recorded on the CRF. During the informed consent process, the subject will be informed that representatives of the Sponsor, IRB/EC, or regulatory authorities may inspect, review, and photocopying of the subject records and that all personal information will be maintained in strict confidence and in accordance with local data protection requirements and/or laws. In the event a subject's data are used for educational, presentation, and/or publication purposes, subject identity will be masked to protect the subject's confidentiality.

### 10.2 Protocol Deviations

The investigator must adhere to all specifications defined in this protocol. The study investigator should not deviate from the protocol, unless the study plan poses unacceptable risks to the health or welfare of the involved individual subject. The investigator shall notify Channel Medsystems Inc. and the reviewing ethics committee of any deviation from the protocol intended to protect the life or physical wellbeing of a subject in an emergency. Such notice shall be given as soon as possible, but in no event later than five working days after the emergency occurred. Except in such an emergency, prior approval of Channel Medsystems Inc. is required for any deviation from the protocol. Approval from the IRB/EC also is required if these changes or deviations are expected to affect the rights, safety or welfare of human subjects.

### 10.3 Investigator Reports

Investigators are required to prepare and submit the following complete, accurate and timely reports on this investigation (See Table below)

**Table 4: Responsibilities for Submitting Reports and Other Data**

Type of Report	Prepared by Investigator For	Time of Notification
Informed Consent Not Obtained From Subject	Sponsor, IRB/EC	Within 5 working days
Device Malfunction	Sponsor Return device to Sponsor	Within 5 working days of malfunction
Device Malfunction associated with an SAE	Sponsor, Health Canada*	In Canada: Within 72 hours of occurrence
Serious Adverse Event (Including death) Notification	Sponsor, IRB/EC**	Within 24 hours of knowledge of event**
Unanticipated Adverse Device Events (UADE) Notification	Sponsor	Within 24 hours of knowledge of event
Unanticipated Adverse Device Event (UADE) Report	Sponsor, IRB/EC	Within 10 working days of knowledge of event
Serious Adverse Event Written Report	Sponsor, IRB/EC**	Within 5 working days of knowledge of event to the Sponsor and according to IRB/EC policy to the IRB/EC
Subject Withdrawal	Sponsor	Within 5 working days of withdrawal
Withdrawal of IRB/EC approval	Sponsor	Within 5 working days of withdrawal
Major deviation from the Investigational Plan, protecting life or physical wellbeing of subject	Sponsor, IRB/EC	Within 5 working days of deviation
Progress Report	Sponsor, IRB/EC	At a minimum, annually
Final Report	Sponsor, IRB/EC	Within 3 months of study completion

\* Reporting requirement specific to Canadian study centers

\*\* Notification to be made according to local and/or central IRB/EC policy.

#### 10.4 Record Retention

For clinical sites in the United States, the investigator should retain all study records and reports for a minimum of six (6) years. For clinical sites in Canada, the investigator should retain all study records and reports for a minimum of twenty five (25) years. For other countries, the clinical site should retain records for a minimum of two (2) years or according to local requirements or regulations if longer. To avoid error, the Investigator should contact the Sponsor before the destruction of any records and reports pertaining to the study to ensure they no longer need to be retained. In addition, the investigator should contact the sponsor if he/she plans to leave the investigational site so that arrangements can be made for transfer of records.

## **1.0 Introduction**

This is a pivotal trial to evaluate the effectiveness of the Cerene device to treat heavy menstrual bleeding. This is a single arm trial that will enroll a maximum of 242 patients. The primary endpoint is the pictorial blood loss assessment chart (PBLAC) at 12 months after treatment. Patients who achieve a PBLAC score of  $\leq 75$  will be considered responders. The proportion of patients achieving a response will be compared against an objective performance criterion (OPC) of 66%. This trial will be monitored for early success.

## **2.0 Statistical Modeling**

We use a longitudinal model that considers the PBLAC as continuous to allow the earlier observations of PBLAC to predict the final 12-month PBLAC value. The primary analysis is based on the dichotomized PBLAC score at 12 months where values less than or equal to a 75 indicate response.

### *2.1 Longitudinal Model*

Patients will be assessed at 3, 6, and 12 months following treatment. We use a longitudinal model of the primary endpoint to allow these earlier observations to predict the final 12-month status. The primary endpoint for an individual patient,  $i$ , at time  $t$  is labeled as  $Y_{it}$ . At each interim analysis, some patients will have completed follow-up and we will have observed their 12-month endpoint  $Y_{i12}$ . These patients may also have earlier measures of the primary endpoint, such as at 3 and 6 months. There will be patients with earlier observations of the primary endpoint who have not yet reached 12 months of follow-up. We utilize the information from patients with incomplete follow-up to the extent that these earlier observations are correlated with the final 12-month value. A Bayesian model is built to learn how the early endpoints are correlated with the final 12-month endpoint and patients with complete follow-up information this model.

A linear regression model is created for the correlation between the baseline and 12-month, 3-month and 12-month, and 6-month and 12-month values. We suppress the subject index  $i$  and refer to the baseline, 3, 6, and 12 month values as  $Y_0, Y_3, Y_6$ ,

and  $Y_{12}$ . There are three instances of the model. We model the log PBLAC score and each model instance is identical and has the following structure

$$\left[ \log(Y_{12}) | \log(Y_0) \sim N(\alpha_0 + \beta_0 \log(Y_0), \lambda_0^2) \right]$$

$$[\alpha_0] \sim N(1, 2^2)$$

$$[\beta_0] \sim N(0.5, 1.5^2)$$

$$[\lambda_0^2] \sim IG(0.6, 1)$$

Identical models and prior distributions are assumed for the distribution of  $Y_{12}$  given  $Y_3$  and for  $Y_{12}$  given  $Y_6$

The joint posterior distribution of  $\alpha_0, \alpha_3, \alpha_6, \beta_0, \beta_3, \beta_6, \lambda_0, \lambda_3$ , and  $\lambda_6$ , is updated based on all patients with observed values of  $Y_{12}$ . This model is then used (using Bayesian imputation within Markov chain Monte Carlo) to inform the primary analysis.

## 2.2 Primary Efficacy Analysis

Let  $I_{i12}$  be the response indicator for the  $i^{\text{th}}$  patient at 12 month.  $I_{i12}$  will be 1 where  $Y_{i12}$  is less than or equal to 75 and will be 0 where  $Y_{i12}$  is greater than 75. Let  $\pi = \Pr(I_{i12} = 1)$  be the probability of response at 12 months. We model the log odds of response,

$$\theta = \log(\pi/1-\pi)$$

as normally distributed with prior a distributions for the log-odds of response

$$\theta \sim N(0, 2^2),$$

When converted from the log-odds scale back to the original probability scale, the resulting prior distribution for the log odds of response has a median of 50% and a 95% probability that the success rate is between 2% and 98%.

The longitudinal modeling will be used to inform the early success analyses at each planned interim analysis. However, consistent with the ITT population definition that the 66% OPC is based on, any patients with missing 12 month values for the primary endpoint will be considered non-responders in the primary efficacy analysis. Therefore, the longitudinal modeling will have no impact on the final primary efficacy analysis.

### 3.0 Allocation

A maximum of 242 patients will be enrolled and treated. This is a single arm trial and all enrolled patients will be treated with the Cerene device.

### 4.0 Evaluation of Trial Success

Interim analyses are planned when 100 and when 175 patients have been enrolled and treated and in the trial for 12 months, i.e. when the first 100 and 175 patients have had the opportunity to complete follow-up for the 12-month primary endpoint.

At an interim analysis, early success will be declared if there is a high probability that the response rate with the Cerene device is superior to the OPC of 66%. Formally if:

$$\Pr(\pi > 0.66) > 0.979.$$

A final determination of trial success will be applied when all 242 patients have the opportunity to complete follow-up for the 12-month primary endpoint. Even if early success is declared, a final analysis will be conducted when all 242 patients have the opportunity to complete follow-up. If, at the completion of the trial, there is at least a 97.9% probability the Cerene device is superior to the OPC of 66%, this trial will be considered a success,

$$\Pr(\pi > 0.66) > 0.979.$$

### 5.0 Example Trials

In this section we present a single simulated trial to illustrate the statistical design of the trial.

When the first interim analysis is conducted, all 242 patients have been enrolled and treated and the first 100 patients have completed the 12-months of follow-up for the primary endpoint. We impute 12-month outcomes for the 142 patients still in follow-up based on their earlier visits. For all of these patients we have observed their 6-month visit and so we impute their 12-month outcome based on that most recent visit.

Among the 100 patients with complete follow-up, we have observed a 79% response rate at 6 months and an 80% response rate at 12 months. Among patients still in follow-up, we have observed an 84% response rate at 6 months. By the

longitudinal model, we estimate the 12-month response rate to be 77% (95% Interval = 63.2%, 87.4%). There is a 94% probability that the response rate is greater than the OPC of 66%. This is less than the 97.9% required for early success and the trial continues to the next interim analysis.

	Completers N = 100		Patients in Follow-up N = 142	
	Mean PBLAC Score (SD)	% Response	Mean PBLAC Score (SD)	% Response
Baseline	605 (1198)	25%	747 (1984)	25%
3 Months	80 (95)	66%	82 (100)	67%
6 Months	49 (53)	79%	44 (46)	84%
12 Months	54 (54)	80%	--	--

At the next interim analysis there is complete 12-month follow-up for 175 patients. We now observe a 12-month response rate of 78% among these patients. For the 67 patients still in follow-up, 88% are responders at 6-months. The estimated response rate at 12-months including all patients is 78% (95% Interval = 68.9%, 85.8%). There is a 99.7% probability that this response rate is greater than the OPC of 66%. This trial satisfies the early success criteria.

	Completers N = 175		Patients in Follow-up N = 67	
	Mean PBLAC Score (SD)	% Response	Mean PBLAC Score (SD)	% Response
Baseline	742 (1872)	24%	493 (817)	27%
3 Months	79 (94)	65%	89 (113)	71%
6 Months	49 (53)	80%	37 (30)	88%
12 Months	55 (57)	78%	--	--

At the final analysis of this trial, when all patients have complete follow-up through 12 months, the response rate is 78.4% (95% Interval = 73.1%, 83.5%) and there is a >99% probability that this response rate is greater than the OPC of 66%.

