#### **4.1.8.5 Operating Characteristics**

In order to determine the performance of this trial design, we simulated it 5000 times across various assumptions for the PBLAC over time. Under the null hypothesis, that response rate is the same as the OPC, 66%, this trial will declare success with 2.5% probability. This is the simulated one-sided Type I error rate in this scenario. Under an alternative hypothesis, that the response rate is 75%, this trial will declare early success with approximately 30% probability. The total probability of trial success in this scenario is 87%. This is the power of the trial in this scenario. There is less than a 1% probability that a trial that qualifies an early success would not still be successful at the final analysis with complete data.

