## 7.0 Operating Characteristics

Table 7.1 shows the operating characteristics of the trial design. Results are based on at least 5000 simulations for each scenario. We show the probability of achieving early success and the probability the trial does not achieve an early success but claims success at trial completion (Probability of late success). The total probability of success is the sum of achieving a success, either early or late. All patients are expected to be treated at the time the first interim analysis occurs so the trial's mean sample size is 242 patients.

The operating characteristics presented here are based on the response scenarios in which the SD of the log PBLAC is 0.95. The longitudinal profile of the virtual patients is based on scenarios with a high baseline score and more patients achieving a response at 6 months than at 12 months (Table 6.2.1 mean scenario 1), a high variance for the PBLAC at earlier timepoints (Table 6.6.1 variance scenario 2), and the stronger visit-to-visit correlation. Based on patient-level data from a previous trial of the Cerene device, this is the expected profile of patients who will be enrolled and treated in this trial. We show results across the various assumptions for the proportion of patients dropping-out before 12 months. Operating characteristics based on other simulation scenarios are shown in the appendix.

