**Table 7.1: Operating Characteristics**

Response Among 12-Month Completers	ITT Response	Pr (Early Success)	Pr (Late Success)	Total Pr (Success)
No Drop-Outs				
60%	60.0%	0	0.000	0.000
**66%	66.0%	0.000	0.025	0.025
70%	70.0%	0.015	0.230	0.245
75%	75.0%	0.295	0.571	0.866
80%	80.0%	0.900	0.098	0.998
85%	85.0%	0.999	0.001	1.000
90%	90.0%	1.000	0.000	1.000
5% Drop-Out				
60%	57.0%	0	0	0
66%	62.7%	0	0.001	0.001
70%	66.5%	0.001	0.038	0.039
75%	71.3%	0.044	0.357	0.401
80%	76.0%	0.483	0.441	0.924
85%	80.8%	0.966	0.034	0.999
90%	85.5%	0.999	0.000	0.999
10% Drop-Out				
60%	54.0%	0	0	0
66%	59.4%	0	0	0
70%	63.0%	0	0.001	0.001
75%	67.5%	0.003	0.067	0.070
80%	72.0%	0.105	0.391	0.497
85%	76.5%	0.643	0.303	0.947
90%	81.0%	0.988	0.012	1.000

\*\*10,000 simulations

If the response rate is less than the OPC, 60%, there is a 0% probability of trial success. Under the null hypothesis, that response rate is the same as the OPC, 66%, this trial will not achieve early success, but will achieve success with complete follow-up on all patients with 2.5% probability. This is the simulated one-sided Type I error rate in this scenario. Given that the final evaluation of trial success is based on the dichotomous responses endpoint with complete data among all enroll patients, and that the longitudinal model has no role in the primary efficacy analysis, the overall Type I error rate does not depend on the mean or standard deviation of the PBLAC score, accrual rates, or longitudinal profile assumptions. The simulated Type I error rate here is shown to be controlled to < 2.5% with a critical value of

97.9%, but given there is a single final evaluation of trial success based on complete data, a critical value of 97.5% could also be considered appropriate.

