Under an alternative hypothesis, that the response rate is 75%, this trial will stop early for success with approximately 30% probability. The total probability of trial success in this scenario is 87%. This is the power of the trial in this scenario. As the drop-out rate increases, the observed response rate at 12 month decreases and patients who are missing their 12 month observation are counted as non-responders. Correspondingly, the power of the trial decreases. If 5% of patients drop-out and there is an 80% response rate among completers at 12 months, the response rate in the ITT population will be 76% and there is a 92.4% probability of trial success. If 10% of patients drop-out and there is an 85% response rate among completers at 12 months, the response rate in the ITT population will be 76.5% and there is a 94.7% probability of trial success.

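### The interim model written in SAP 2.1–2.2 does not reproduce the SAP's interim example, the early-success figures in Table 7.1, or the protocol's reversal figure

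*SAP*

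**What the plan says.** SAP 2.1 regresses log 12-month PBLAC on the log of an earlier PBLAC, with stated priors, and learns the relation from women whose 12-month value is known. "This model is then used (using Bayesian imputation within Markov chain Monte Carlo) to inform the primary analysis". SAP 2.2 puts a N(0, 2²) prior on the log-odds of response. SAP 4.0 declares early success, at 100 and at 175 women with 12-month opportunity, if Pr(π > 0.66) exceeds 0.979.

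SAP 5.0 works an example.

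- **First interim.** Among 100 completers, "we have observed a 79% response rate at 6 months and an 80% response rate at 12 months". The other 142 women have 84% response at 6 months. The result is given by the "longitudinal model, we estimate the 12-month response rate to be 77% (95% Interval = 63.2%, 87.4"%), with probability 94%, so the trial continues.
- **Second interim.** There are 175 completers with 78% response. "The estimated response rate at 12-months including all patients is 78% (95% Interval = 68.9%, 85.8"%), with probability 99.7%.
- **Final analysis.** 78.4% (73.1%, 83.5%).

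Table 7.1, without drop-out, gives early success of 0.000, 0.015, 0.295 and 0.900 at true rates of 66, 70, 75 and 80%. The text of SAP 7.0 says that at 66% "this trial will not achieve early success, but will achieve success with complete follow-up on all patients with 2.5% probability", and that at 75% "this trial will stop early for success with approximately 30% probability". On how the columns combine: "The total probability of success is the sum of achieving a success, either early or late". Protocol 4.1.8.5 repeats the 30% and adds that there is "less than a 1% probability that a trial that qualifies an early success would not still be successful at the final analysis".

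**The concern.** The first-interim result looks impossible on its face. Adding 142 partly observed women, whose 6-month response is better than that of the completers, should tighten the interval that the completers give alone, or at worst leave it about the same. The SAP reports a wider one, and the extra width turns a clear early success into a failure to declare.

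Protocol 4.1.6 ties an early marketing application to this rule.

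- If the written model is run, early claims will be far more frequent than the plan states, and more of them will later reverse.
- If the simulated code is run, the tables may be right, but SAP 2.1–2.2 does not specify it, and nobody could reproduce the interim from the plan.

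While the two disagree, the choice between materially different interim rules could be made after data are seen.

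**Working it through.** **Inputs.** Prior θ = logit(π) ~ N(0, 2²) (SAP 2.2). Cut 0.979, looks at 100 and 175, total 242 (SAP 4.0). Example counts from SAP 5.0. Regression priors α ~ N(1, 2²), β ~ N(0.5, 1.5²), λ² ~ IG(0.6, 1), read as shape 0.6 and scale 1 (SAP 2.1). Expected profile (SAP 6.1, 6.2, 7.0): log SD 0.95; 6-month mean multiplier 0.96 and variance multiplier 1; 6-to-12-month correlation 0.6; log means 3.925, 3.82, 3.676 and 3.518 for 66, 70, 75 and 80%.

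**Step 1: reproduce the final analysis.** With s responders of n, the posterior of θ is proportional to π^s (1−π)^(n−s) exp(−θ²/8). For 190/242 (78.5%) this gives mean 78.4%, interval 73.0–83.3%; stated 78.4% (73.1–83.5%). Success needs 175/242 (Pr 0.982; 174 gives 0.975). Exact binomial success at the final analysis is 0.0211 at 66% and 0.850 at 75%. Prior, cut and data are therefore being read as the SAP intends.

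**Step 2: the interims from completers alone, no imputation.**

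| Look | Completers | Computed interval | Pr(π > 0.66) | Stated interval | Stated Pr |
|---|---|---|---|---|---|
| 1 | 80/100 | 71.3–86.9% | 0.999 | 63.2–87.4% | 0.94 |
| 2 | 137/175 | 71.7–83.9% | >0.999 | 68.9–85.8% | 0.997 |

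(78% of 175 also fits 136, which gives 71.1–83.4%.)

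**Step 3: how much data the stated intervals represent.** Take s = [logit(upper) − logit(lower)]/3.92 and n ≈ 1/[s² m(1−m)], with m the stated rate.

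- Look 1: s = 0.356, n ≈ 1/(0.356² × 0.77 × 0.23) ≈ 44.5. Direct check: 77% of 44 women gives 63.1–87.3%, Pr about 0.94.
- Look 2: s = 0.256, n ≈ 89, although 175 are complete.
- Final: s = 0.159, n ≈ 235, close to 242.

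**Step 4: early success from completers only, exact.** The cut needs 76/100 (Pr 0.984; 75 gives 0.973) or 129/175 (0.986; 128 gives 0.978). At a true 75% the first look alone passes with probability 0.46, and either look with 0.72. Table 7.1 says 0.295.

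**Step 5: the full written model.** A Gibbs sampler fits log(Y12) on log(Y6) to completers with the SAP priors. At each draw the pending outcomes are imputed, and Pr(π > 0.66) on all 242 is averaged over draws. Only 6-month values are needed, because SAP 5.0 has every pending woman past 6 months. Trials: 40,000 at 66%; 20,000 at each other rate.

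| True rate | Early, stated | Completers only, exact | Written model | Early successes that fail at the end | Same, share of all trials |
|---|---|---|---|---|---|
| 66% | 0.000 | 0.031 | 0.020 | 412/803 = 51% | 1.0% |
| 70% | 0.015 | 0.201 | 0.199 | 1,067/3,969 = 27% | 5.3% |
| 75% | 0.295 | 0.721 | 0.804 | 789/16,085 = 4.9% | 3.9% |
| 80% | 0.900 | 0.985 | 0.997 | 16/19,937 = 0.08% | 0.08% |

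At 66%, success at the final analysis alone was 2.2%. Adding early successes that reverse gives 2.2% + 1.0% = 3.2% for early or late.

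A second implementation gave 0.019, 0.197, 0.794 and 0.996, with 4.4% reversal at 75%. At 66% it gave 59% reversal, so that share is less stable.

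**Step 6: robustness at 75%.** Over 48 combinations of the SAP's log SDs and 6-month mean, variance and correlation scenarios, early success ran from 0.745 to 0.826 and reversal from 2.3% to 6.1%. With zero 6-to-12-month correlation, early success is 0.774. Other readings of the model at the 0.979 cut also miss 0.295: raw-scale regression 0.57, baseline-only regression 0.77, λ² used as a standard deviation 0.88, one residual shared by all imputed women 0.00. A cut between 0.999 (early success 0.351) and 0.9995 (0.272) comes near, but a stricter cut cannot explain SAP 5.0, where the reported probability is itself 0.94.

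**The case against.** The strongest reply is that little depends on the interim. All 242 women are expected to be treated before the first look. A final analysis follows whatever the interim shows, and SAP 2.2 keeps the longitudinal model out of it. The only stated consequence of early success is an approach to the regulator. This stands as a limit on the harm: final power, final type I error, treatment and follow-up are unaffected. It does not make the interim rule reproducible.

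Second, the 3.2% is not the type I error of the final test. SAP 4.0 places trial success at the final analysis, and SAP 7.0 ties the error rate to that single evaluation, where the exact value is 2.1%. That is right. The 3.2% is the chance of any success declaration, and is relevant because SAP 7.0 defines its total column as early or late.

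Third, not every row is shown to be wrong. The 60% row agrees, the 85% and 90% rows without drop-out are near ceiling, and the drop-out rows were only spot-checked because interim handling of drop-outs is not fully specified. The demonstrated mismatch is in the 66–80% rows without drop-out. The protocol also names no true rate for its reversal figure, which holds at 80%, though it directly follows the 75% scenario.

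Fourth, the final figures match closely but not perfectly. At 75% the stated total is 0.866. The exact final value plus the largest allowed reversal is 0.850 + 0.01 × 0.295 = 0.853, about 2.6 simulation standard errors lower at 5,000 runs. This small gap is unexplained and does not bear on the interim discrepancy.

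Finally, SAP 7.0 cites an appendix that is not in the file. It is described as results for other scenarios, so it is unlikely to supply the missing model component.

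**Conclusion.** The concern holds. The first-interim example contradicts the written rule using only the SAP's prior, its cut and its 80/100 completers, with no assumption about patient-level data: 0.999 passes and the SAP reports 0.94. At a true 75%, early success under the written model is about 0.80 against a stated 0.295, and 4–5% of early successes reverse against a stated figure below 1%. The simulated figures rest on the SAP's expected profile, no drop-out, and the shape–scale reading of the inverse-gamma prior. No SAP profile tried brings early success near 0.295.

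SAP 5.0 and Table 7.1 are consistent with each other: both behave as if the interim carried much more variance than SAP 2.1–2.2 describes. No passage available mentions a discount or added variance, so the documents cannot show whether the text omits a component or the code is wrong. If the code is what will be run, the effect is conservative: early claims come later but are not lost. The discrepancy must be resolved before the first interim, because the two versions give opposite decisions on the same data.

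**What to change.** Before the first interim, compare the coded interim model with SAP 2.1–2.2 and take one of two routes.

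1. **Keep the code.** Amend SAP 2.1–2.2 to state the model and cut actually simulated, including the source of the extra interim variance. SAP 5.0 and Table 7.1 may then stand.
2. **Keep the text.** Run the written model and re-issue the SAP 5.0 example, the early, late and total columns of Table 7.1, the early-success statements in SAP 7.0, and the 30% and under-1% figures in Protocol 4.1.8.5.

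On either route, give the true response rate at which the reversal figure applies, and whether it is a share of early successes or of all trials.

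The cost is SAP wording or a simulation re-run, plus a matching protocol edit on the second route. Nothing changes for patients, the sample size or the final success rule.
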